1.9.4 To Assess Effect of PD 0332991 on Markers of Tumor Cell Senescence

Studies in preclinical models of ER+ breast cancer indicated that PD 0332991 induced stable cell cycle arrest that was fundamentally distinct from those elicited by ER antagonists and was capable of inducing aspects of cellular senescence, as measured by expression of senescence-associated b-galactosidase [20]. In addition, candidate proteins important for senescence including p16, IL6, cyclin D1, activated mTOR (such as pS6), FOXM1 phosphorylation, will be examined [19, 101]. These markers will be assayed on tumors collected at all time points. Since surgery occurs after at least 3 weeks after the last dose of PD 0332991, a comparison of these markers as well as Ki67 level between surgery and C1D15 sample will be informative in determining whether 4 months of combination therapy induced irreversible cell cycle arrest and cells have entered senescence.

1.9.5 Evaluation of Target Inhibition on the Cdk4/6-Rb Pathway

The pharmacodynamic effect of PD 0332991 in combination with anastrozole on the Cdk4/6-Rb pathway activities will be assessed by phosphoproteomics and immunohistochemistry analysis on serial tumor biopsies. Since PD 0332991 inhibits Cdk4/6 phosphorylation of Rb at Ser^{801/811} and Ser⁷⁸⁰, the levels of total and phosphorylated RB will be examined at baseline, post 1 cycle of single agent anastrozole, then post 2 weeks of PD 0332991 in combination with anastrozole.

1.9.6 Preoperative Endocrine Prognostic Index (PEPI)

In a multivariable analysis conducted on the P024 trial, three other post-neoadjuvant endocrine therapy tumor factors were determined to have independent prognostic value for relapse and death after relapse in addition to Ki67 [11]. These included pathological tumor size (T1/2 versus T3/4), pathological node status (positive or negative), the natural logarithm of the Ki67 value and the ER status of the tumor. A prognostic score, the preoperative endocrine prognostic index (PEPI),

was developed, which weighs each of these factors according to their associated hazard ratios. PEPI was then validated in an independent data set from the IMPACT trial [11]. No relapses were recorded in either trial in patients with T1, N0 tumors with a PEPI score of 0 (residual tumor with Ki67 index of 2.7% - natural logarithm of 1- or less with maintained ER expression) or in the rare patient with a pCR. PEPI has also recently been validated in the POL Trial (PreOperative Letrozole trial: A multicenter phase II trial of letrozole in postmenopausal women with clinical stage II or III hormone receptor positive breast cancer) [13]. In the combined analysis of P024 trial/POL trial, no relapse was observed with a median follow up of 61.3 months in the 24 patients in the PEPI 0 category. PEPI 0 as a prognostic marker on therapy therapy is being validated prospectively in the A011106 trial. An improvement in the rate of PEPI 0 following neoadjuvant PD 0332991 and anastrozole compared to the historical control would be of great interest for the design of adjuvant trials of PD 0332991.

1.9.7 Assessment of Serum Estradiol Level Before and Following PD 0332991

The goal of this study is to ensure that PD 0332991 does not interact with anastrozole in reducing serum estradiol levels in addition to monitor changes in estradiol in premenopausal women being treated with goserelin, anastrozole before and after PD 0332991 during the course of therapy. Since there are no obvious theoretical pharmacokinetic interactions between the two agents, we do not anticipate a change in serum estradiol levels following PD 0332991 administration. Blood will be collected from premenopausal women for sensitive estradiol measurement, to be done at the clinical laboratory, at baseline, end of 4 weeks of anastrozole (or in combination with goserelin), Cycle 3 Day 1, and at time of surgery. In patients on goserelin because of initial premenopausal status prior to pre-registration, estradiol level must be in the postmenopausal range per institutional standard after Cycle 0 therapy to be eligible for the study drug therapy on this trial. In addition, these patients should go off study drug therapy and be considered inevaluable for the primary endpoint if the estradiol level rose to premenopausal range on Cycle 3 Day 1 or at Surgery or any time during Cycles 1-4 of treatment.

2.0 OBJECTIVES

Since surgery occurs 3 to 5 weeks following the last dose of PD 0332991 in order to avoid complications related to PD 0332991-induced myelosuppression, we propose to assess the primary endpoint of complete cell cycle arrest (Ki67 \leq 2.7%) on C1D15 while patients are receiving PD 0332991. The value of Ki67 on C1D15 and at surgery will provide data on the potential reversibility of Ki67 decrease when off PD 0332991 for at least 3 weeks. These data may help to hypothesize regarding the duration of the biologic effect of PD 0332991.

Amendment #5:

Please note that as of Amendment #5, a fifth cycle of daily PD 0332991 (consisting of 10-12 days of treatment, plus continued daily anastrozole) is added prior to surgery based on preliminary analysis of the first 18 patients showing an increase in tumor Ki67 at the time of surgery which was performed 3 to 5 weeks after the last dose of PD 0332991 (Cycle 4 Day 21). This data indicates that PD 0332991 has a reversible effect on cell cycle arrest. However, alternative explanations exist—for example, the emergence of resistance clones. To investigate these possibilities, we propose to re-initiate PD 0332991 (and continue anastrozole) for patients whose blood counts and other AEs recover sufficiently after 4 complete neoadjuvant cycles of PD 0332991 + anastrozole, and treat for an additional 10 to 12 days, with the last dose of PD 0332991 and anastrozole being administered on the day before surgery. Based on previous phase I studies, the mean ANC within 10-12 days of treatment is between 2.2 k-4.2 k/mcL (personal communication with Pfizer), therefore we expect majority of our patients will be able to complete Cycle 5. In fact, a neoadjuvant study consisting of 14 days of aromatase inhibitor +/- PD 0332991 before surgery is ongoing, and none of the first 9 patients randomized to receive PD 0332991 had ANC < 1,000 on Day 10 (personal communication with Pfizer).

2.1 Primary Objective

1. To determine the rate of complete cell cycle arrest, defined by Ki67 $\leq 2.7\%$, following 2 weeks (C1D15) of neoadjuvant PD 0332991 in combination with anastrozole in women with clinical stage II or III ER+/HER2- breast cancer without PIK3CA hot spot mutation (PIK3CA Wild Type Cohort).
2. To determine the rate of complete cell cycle arrest, defined by Ki67 $\leq 2.7\%$, following 2 weeks (C1D15) of neoadjuvant PD 0332991 in combination with anastrozole in women with clinical stage II or III ER+/HER2- endocrine-resistant breast cancer.

2.2 Secondary Objectives

1. To determine the rate of complete cell cycle arrest, defined by Ki67 $\leq 2.7\%$, following 2 weeks (C1D15) of neoadjuvant PD 0332991 in combination with anastrozole in women with clinical stage II or III ER+/HER2- breast cancer with PIK3CA hot spot mutation.
2. To determine the rate of complete cell cycle arrest, defined by Ki67 $\leq 2.7\%$, following 2 weeks (C1D15) of neoadjuvant PD 0332991 in combination with anastrozole in women with clinical stage II or III ER+/HER2- endocrine-resistant breast cancer.

The following objectives will be assessed in PIK3CA mutant cohort and in PIK3CA Wild Type (WT) cohort combined or separately, and assessed separately in the endocrine resistant cohort.

3. To compare the rate of complete cell cycle arrest between C1D1 and C1D15

4. To assess Ki67 level on serially collected tumor specimens (baseline, C1D1, C1D15, and surgery)
5. To determine the rate of PEPI 0 score with the study drug therapy
6. To determine the pathologic complete response (pCR) rate of study drug therapy
7. To assess the rate of clinical response and radiologic response in the neoadjuvant setting
8. To determine the safety profile (on therapy and post 30 days of therapy completion) of the study therapy during 4 months of neoadjuvant therapy.
9. To determine the safety profile of the study therapy during 2 years of adjuvant therapy.
10. To assess the long term outcomes of patients treated in this trial.

2.3 Exploratory Objectives

The following objectives will be assessed in PIK3CA mutant cohort and in PIK3CA WT cohort combined or separately, and assessed separately in the endocrine resistant cohort.

1. To assess tumor cell apoptosis index and senescence markers on serially collected tumor specimens
2. To examine the pharmacodynamic effect of PD 0332991 in combination with anastrozole using serially collected tumor specimens (baseline, C1D1, 2 weeks on combination therapy, and surgery)
3. To explore molecular mechanisms which could affect tumor response to the combination PD 0332991 and anastrozole by tumor genomic, transcriptomic, and proteomic analysis
4. To document pathologic staging (tumor size, lymph node status) following neoadjuvant chemotherapy in patients who had tumor Ki67>10% on C1D15 and elected to receive neoadjuvant chemotherapy
5. To explore circulating markers predictive of cancer recurrence.
6. To assess the concentrations of anastrozole prior to and 90 minutes following anastrozole (without PD 0332991) on Cycle 1 Day 1 and to compare these concentrations to the concentrations of anastrozole prior to and 90 minutes following both anastrozole and PD 0332991 on Cycle 1 Day 15.
7. To assess the concentration of PD 0332991 prior to and 90 minutes following both

anastrozole and PD 0332991 on Cycle 1 Day 15.

3.0 PATIENT SELECTION

There are three cohorts of patients for this trial: 1) PIK3CA Wild Type Cohort, 2) PIK3CA Mutant Cohort, and 3) Endocrine Resistant Cohort. **As of Amendment #7, enrollment to the PIK3CA Wild Type and Mutant Cohorts is closed; patients may enroll to the Endocrine Resistant Cohort for neoadjuvant treatment and to the Adjuvant Cohort for adjuvant treatment.**

Applicable to the PIK3CA Wild Type and Mutant Cohort:

Patients who were pre-registered to NCI 9170 trial (Phase II Trial of Neoadjuvant MK-2206 in Combination with either Anastrozole if Postmenopausal or Anastrozole and Goserelin if Premenopausal in Women with Clinical Stage 2 or 3 PIK3CA Mutant Estrogen Receptor Positive and HER2 Negative Invasive Breast Cancer), started anastrozole (or anastrozole plus goserelin if premenopausal) \leq 6 weeks, and were found negative for PIK3CA hotspot mutations are eligible to be screened for the wild type cohort.

In institutions without NCI9170 open, or after completion of enrollment to NCI9170 in institutions where it is open, patients will be pre-registered to this trial and those with PIK3CA mutations will be enrolled to the PIK3CA mutant cohort.

Applicable to the Endocrine Resistant Cohort:

Pre-registration is not required for patients to be enrolled in the endocrine resistant cohort, as PIK3CA mutation status will not be assessed for those patients.

Patients who are potentially eligible to receive adjuvant treatment with PD 0332991 are required to be screened using the eligibility criteria in Section 3.5.

3.1 Pre-registration Eligibility Criteria for the PIK3CA Mutant Cohort

Note: enrollment to this cohort is CLOSED as of Amendment #7.

3.1.1 Inclusion Criteria

1. Clinical T2-T4c, any N, M0 invasive ER+ (Allred Score of 6-8) and HER2 negative (0 or 1+ by IHC or FISH negative for amplification) breast cancer, by AJCC 7th edition clinical staging, with the goal being surgery to completely excise the tumor in the breast and the lymph node.

Note: Patients with invasive ER+ (Allred Score of 6-8) HER2- breast cancer or DCIS in the contralateral breast the patient are eligible

2. Female \geq 18 years of age.
3. ECOG performance status of 0, 1 or 2 (Appendix A).

4. Life expectancy > 4 months.
5. If premenopausal, patient must be willing to comply with pregnancy requirements laid out in Section 5.5.
6. Adequate organ and marrow function as defined below:
 - a. leukocytes \geq 3,000/mcL
 - b. absolute neutrophil count \geq 1,500/mcL
 - c. platelets \geq 100,000/mcL
 - d. total bilirubin \leq upper normal institutional limits
 - e. AST(SGOT)/ and ALT(SGPT) \leq 2.5 X institutional upper limit normal
 - f. Creatinine \leq upper normal institutional limits
7. Able to understand and willing to sign an IRB-approved written informed consent document.

3.1.2 Exclusion Criteria

1. Prior treatment of this cancer including:
 - a. Surgery,
 - b. Radiation therapy,
 - c. Chemotherapy,
 - d. Biotherapy,
 - e. Hormonal therapy
 - f. Investigational agent prior to study entry.
2. Receiving any other investigational agents.
3. Prior therapy with any Cdk4 inhibitor.
4. Any of the following in the previous 6 months:
 - a. myocardial infarction
 - b. severe/unstable angina
 - c. coronary/peripheral artery bypass graft
 - d. symptomatic congestive heart failure
 - e. cerebrovascular accident
 - f. transient ischemic attack
 - g. symptomatic pulmonary embolism.
5. Uncontrolled intercurrent illness including, but not limited to:
 - a. ongoing or active infection
 - b. symptomatic congestive heart failure
 - c. unstable angina pectoris
 - d. uncontrolled symptomatic cardiac arrhythmia,
 - e. psychiatric illness/social situations that would limit compliance with study

requirements.

6. Pregnant/nursing.
7. Unwilling to employ adequate contraception.
8. Known HIV-positive on combination antiretroviral therapy.

NOTE: HIV-positive patients on combination antiretroviral therapy are ineligible because of the potential for pharmacokinetic interactions with PD 0332991. In addition, these patients are at increased risk of lethal infections when treated with marrow-suppressive therapy.

9. Evidence of inflammatory cancer (clinical presentation of skin erythema involving more than one third of the breast or pathological evidence of dermal lymphatic involvement)
10. Known metastatic disease.
11. Current use of anticoagulation therapy.
12. Previous excisional biopsy of the breast cancer or sentinel lymph node biopsy.
13. Any condition that impairs patient's ability to swallow PD 0332991 tablets (e.g., gastrointestinal tract disease resulting in an inability to take oral medication or a requirement for IV alimentation, prior surgical procedures affecting absorption)
14. History of allergic reactions attributed to compounds of similar chemical or biologic composition to PD 0332991 or other agents used in the study.
15. Corrected QT (QTc) interval >470 msec.

3.2 Registration Eligibility Criteria for the PIK3CA Mutant Cohort

Note: enrollment to this cohort is CLOSED as of Amendment #7.

3.2.1 Inclusion Criteria

The criteria below must be met for registration onto the study in addition to the pre-registration criteria, except treatment with endocrine therapy for this cancer is allowed prior to registration.

1. For the PIK3CA mutant cohort: tumor PIK3CA mutation present
2. In premenopausal women, serum estradiol level in postmenopausal range ≤ 7

days prior to registration.

3.2.2 Exclusion Criteria

The criteria below must be met for registration onto the study in addition to the pre-registration criteria.

1. Current use or anticipated need for food or drugs that are known strong CYP3A4 inhibitors (i.e. grapefruit juice, verapamil, ketoconazole, miconazole, itraconazole, posaconazole, erythromycin, clarithromycin, telithromycin, indinavir, saquinavir, ritonavir, nelfinavir, lopinavir, atazanavir, amprenavir, fosamprenavir, nefazodone, diltiazem, and delavirdine) or inducers (i.e. dexamethasone, glucocorticoids, progesterone, rifampin, phenobarbital, St. John's wort).

3.3 Eligibility Criteria for the PIK3CA Wild Type Cohort

Note: enrollment to this cohort is CLOSED as of Amendment #7.

3.3.1 Inclusion Criteria

1. Clinical T2-T4c, any N, M0 invasive ER+ (Allred Score of 6-8) and HER2 negative (0 or 1+ by IHC or FISH negative for amplification) breast cancer, by AJCC 7th edition clinical staging, with the goal being surgery to completely excise the tumor in the breast and the lymph node.

Note: Patients with invasive ER+ (Allred Score of 6-8) HER2- breast cancer or DCIS in the contralateral breast the patient are eligible

2. For the PIK3CA wild type cohort: tumor PIK3CA mutation absent

Note that if a patient did not have sufficient research tissue for PIK3CA sequencing at pre-registration or if PIK3CA sequencing result is delayed, she could be registered and enrolled on the PD991 trial without assigning to a particular cohort at the time of enrollment. PIK3CA sequencing will be performed in the future on tumors collected at subsequent time points to assign the treatment cohort or when the PIK3CA sequencing data is available.

3. For the endocrine resistant cohort: Ki67 > 10% by central testing at Washington University AMP laboratory from a tumor biopsy performed after at least 2 weeks on neoadjuvant endocrine therapy.
 - a. Note that prior neoadjuvant endocrine therapy could include any endocrine therapy (including aromatase inhibitor, tamoxifen, fulvestrant) alone or in combination, or endocrine therapy in combination with any investigational

- agent that is not a Cdk 4/6 inhibitor.
- b. Patients who had a Day 17 Ki67 > 10% from the NCI9170 trial are eligible for the endocrine resistant cohort.
- c. Note that enrollment to the endocrine resistant cohort will depend on the funding availability. Please contact the study chair before enrolling patients to this cohort.

4. Female \geq 18 years of age.
5. ECOG performance status of 0, 1 or 2 (Appendix A).
6. Life expectancy $>$ 4 months.
7. If premenopausal, patient must be willing to comply with pregnancy requirements laid out in Section 5.5.
8. Adequate organ and marrow function as defined below:
 - a. Leukocytes \geq 3,000/mcL
 - b. absolute neutrophil count \geq 1,500/mcL
 - c. platelets \geq 100,000/mcL
 - d. total bilirubin \leq upper normal institutional limits
 - e. AST(SGOT)/ and ALT(SGPT) \leq 2.5 X institutional upper limit normal
 - f. Creatinine \leq upper normal institutional limits
9. In premenopausal women, serum estradiol level in postmenopausal range \leq 7 days prior to registration.
10. Able to understand and willing to sign an IRB-approved written informed consent document.

3.3.2 Exclusion Criteria

1. Prior treatment of this cancer including:
 - a. Surgery,
 - b. Radiation therapy,
 - c. Chemotherapy,
 - d. Biotherapy,
 - e. Hormonal therapy
 - f. Investigational agent prior to study entry.
2. Receiving any other investigational agents.
3. Prior therapy with any Cdk4 inhibitor.
4. Any of the following in the previous 6 months:

- a. myocardial infarction
 - b. severe/unstable angina
 - c. coronary/peripheral artery bypass graft
 - d. symptomatic congestive heart failure
 - e. cerebrovascular accident
 - f. transient ischemic attack
 - g. symptomatic pulmonary embolism.
- 5. Uncontrolled intercurrent illness including, but not limited to:
 - a. ongoing or active infection
 - b. symptomatic congestive heart failure
 - c. unstable angina pectoris
 - d. uncontrolled symptomatic cardiac arrhythmia,
 - e. psychiatric illness/social situations that would limit compliance with study requirements.
- 6. Pregnant/nursing.
- 7. Unwilling to employ adequate contraception.
- 8. Known HIV-positive on combination antiretroviral therapy.

NOTE: HIV-positive patients on combination antiretroviral therapy are ineligible because of the potential for pharmacokinetic interactions with PD 0332991. In addition, these patients are at increased risk of lethal infections when treated with marrow-suppressive therapy.

- 9. Evidence of inflammatory cancer (clinical presentation of skin erythema involving more than one third of the breast or pathological evidence of dermal lymphatic involvement)
- 10. Known metastatic disease.
- 11. Current use of anticoagulation therapy.
- 12. Previous excisional biopsy of the breast cancer or sentinel lymph node biopsy.
- 13. Any condition that impairs patient's ability to swallow PD 0332991 tablets (*e.g.*, gastrointestinal tract disease resulting in an inability to take oral medication or a requirement for IV alimentation, prior surgical procedures affecting absorption)
- 14. History of allergic reactions attributed to compounds of similar chemical or biologic composition to PD 0332991 or other agents used in the study.
- 15. Corrected QT (QTc) interval >470 msec.

16. Current use or anticipated need for food or drugs that are known strong CYP3A4 inhibitors (i.e. grapefruit juice, verapamil, ketoconazole, miconazole, itraconazole, posaconazole, erythromycin, clarithromycin, telithromycin, indinavir, saquinavir, ritonavir, nelfinavir, lopinavir, atazanavir, amprenavir, fosamprenavir, nefazodone, diltiazem, and delavirdine) or inducers (i.e. dexamethasone, glucocorticoids, progesterone, rifampin, phenobarbital, St. John's wort).

3.4 Eligibility Criteria for the Endocrine Resistant Cohort

3.4.1 Inclusion Criteria

1. Clinical T2-T4c at diagnosis or screening, any N, M0 invasive ER+ (Allred Score at least 3 or > 1% ER positivity) and HER2 negative (0 or 1+ by IHC or FISH negative or equivocal) breast cancer, by AJCC 7th edition clinical staging, with the goal being surgery to completely excise the tumor in the breast and the lymph node.

Note: Patients with invasive breast cancer that is ER pos, HER2 neg or equivocal or DCIS in the contralateral breast are eligible; multi-focal diseases are not excluded. The dominant lesion will be followed per protocol.

2. Ki67 > 10% by central testing at Washington University AMP laboratory from a tumor biopsy performed after at least 2 weeks on neoadjuvant endocrine therapy.

If Ki67 is > 10% by local testing, the Ki67 slide and H&E slide need to be reviewed by the study pathologist to confirm eligibility (discuss with Study Chair). For patients external to Washington University, please contact the Washington University coordinator by email so that a screening ID# can be assigned prior to shipment of the slides.

Note that prior neoadjuvant endocrine therapy could include any endocrine therapy (including aromatase inhibitor, tamoxifen, fulvestrant) alone or in combination, or endocrine therapy in combination with any investigational agent that is not a Cdk 4/6 inhibitor.

3. Female \geq 18 years of age.
4. ECOG performance status of 0, 1 or 2 (Appendix A).
5. Pre- or post-menopausal women are eligible

If premenopausal, patient must be willing to comply with pregnancy requirements laid out in Section 5.5 and agrees with GnRH agonist therapy for ovarian suppression during the study.

6. Adequate organ and marrow function as defined below:
 - a. Leukocytes \geq 3,000/mcL
 - b. Absolute neutrophil count \geq 1,500/mcL
 - c. Platelets \geq 100,000/mcL
 - d. Total bilirubin \leq upper normal institutional limits
 - e. AST(SGOT)/ and ALT(SGPT) \leq 2.5 X institutional upper limit normal
 - f. Creatinine \leq upper normal institutional limits
7. Able to understand and willing to sign an IRB-approved written informed consent document.

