4.2 Registration

The information in this section applies to patients enrolling to ALL cohorts.

Patients must not start any protocol intervention prior to registration through the Siteman Cancer Center.

The following steps must be taken before registering patients to this study:

1. Confirmation of patient eligibility by Washington University
2. Registration of patient in the Siteman Cancer Center database
3. Assignment of unique patient number (UPN) if not pre-registered through this trial

Once the patient has been entered in the Siteman Cancer Center database, the WUSM coordinator will forward verification of enrollment via email.

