APPENDIX B: Neoadjuvant PD 0332991: Registration Worksheet

Protocol #:	Neoadjuvant PD 0332991 (HRPO# 201301106)	Patient Initials	_____ - _____ - _____
PI Name:		Institution Name:	
Registering MD name:		Site Number:	
Study Coordinator Name and Email:		Site Telephone #	

Please ensure the following are included with this form: (Please ensure all patient identification information is removed)

Corresponding Source Documentation for Inclusion/Exclusion

Menopausal Status	 Pre/Peri- menopausal	 Postmenopausal
DOB:	____ / ____ / ____	
Zip Code:	____ - ____ - ____ - ____	
Date endocrine therapy initiated:	____ / ____ / ____	
Local Ki67 after at least 2 weeks of endocrine therapy:	_____	
Planned Date Investigational Treatment Initiation:	____ / ____ / ____	
Date of signed informed consent:	____ / ____ / ____	

REGISTRATION INCLUSION CRITERIA		
	1. Clinical T2-T4c at diagnosis or screening, any N, M0 invasive ER+ (Allred Score at least 3 or > 1% ER positivity) and HER2 negative (0 or 1+ by IHC or FISH negative equivocal) breast cancer, by AJCC 7th edition clinical staging, with the goal being surgery to completely excise the tumor in the breast and the lymph node.	
Note: If the patient has invasive breast cancer that is ER pos, HER2 neg or equivocal, or DCIS in the contralateral breast, the patient is eligible. Multifocal diseases are not excluded.		
	2. Ki 67 > 10% by central testing after at least 2 weeks on neoadjuvant endocrine therapy.	
	3. Female \geq 18 years of age.	
	4. ECOG performance status of 0, 1 or 2	ECOG: _____ Date Assessed: _____
	5. If premenopausal, patient must be willing to comply with pregnancy requirements laid out in Section 5.5.	
6. Laboratory Values (Within 14 days of Registration)		
	Leukocytes \geq 3,000/mcL	Screening result: _____
	Absolute Neutrophil Count (ANC) \geq 1,500/mcL	Screening result: _____
	Platelets (Plts) \geq 100,000/mcL	Screening result: _____
	Total bilirubin \leq upper normal institutional limits	Screening result: _____ ULN: _____
	Alanine aminotransferase (ALT) and aspartate aminotransferase (AST) \leq 2.5 x upper limit of normal (ULN)	ALT screening result: _____ ULN: _____ AST screening result: _____ ULN: _____

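### The endocrine-resistant cohort lacks the estradiol entry check used in both PIK3CA cohorts, so a few premenopausal women may have their Day 15 Ki67 read before estradiol is reliably suppressed

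*Combined protocol and SAP*

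**What the plan says.** Section 3.2.1 item 2 (PIK3CA mutant) and Section 3.3.1 item 9 (PIK3CA wild type) carry the same entry line, "In premenopausal women, serum estradiol level in postmenopausal range", with a limit of 7 days before registration.

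For the endocrine-resistant cohort, the only neoadjuvant cohort open since Amendment #7, Section 3.4.1 has no such line. Item 5 asks that a premenopausal woman comply with the pregnancy rules and that she "agrees with GnRH agonist therapy for ovarian suppression during the study". The worksheet that sites complete (Appendix B item 5) has only the first part: "If premenopausal, patient must be willing to comply with pregnancy requirements laid out in Section 5.5".

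Entry needs Ki67 above 10% from a "tumor biopsy performed after at least 2 weeks on neoadjuvant endocrine therapy". The note to that item says that "prior neoadjuvant endocrine therapy could include any endocrine therapy (including aromatase inhibitor, tamoxifen, fulvestrant) alone or in combination".

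Cycle 0 (Section 5.1) and the 28-day endocrine lead-in (10.2 footnote E) are limited to the PIK3CA cohorts. Section 4.2, for all cohorts, says "Patients must not start any protocol intervention prior to registration through the Siteman Cancer Center". Section 5.1 prefers goserelin on Day 1 of each cycle but allows any day.

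Sections 1.6.1 and 1.6.2 say that estradiol first rises on goserelin and reaches postmenopausal levels by three weeks.

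**The concern.** A premenopausal woman can qualify on tamoxifen or fulvestrant without ovarian suppression, register without an estradiol test, and receive her first goserelin on C1D1. Nothing in 3.4.1 or Appendix B prevents this.

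Her C1D15 Ki67 then does two jobs. It is the primary endpoint (15.2), and above 10% it takes her off study drug (9.3.1). It also decides access to adjuvant PD 0332991, which needs Ki67 of 10% or less in this cohort (3.5.1 item 1). If estradiol is not yet suppressed, she may be called resistant, or counted as not arrested, on a reading taken too early.

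The same woman raises a second problem. Her qualifying Ki67 was also read without ovarian suppression, so she may not be resistant to anastrozole plus goserelin. On study she starts new estrogen deprivation together with PD 0332991, and any arrest is credited to the combination against a 5% null. The biopsy before PD 0332991 is waived if a research biopsy was done before registration or an archival block exists (10.2 footnote W), so the two effects need not be separable.

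**Working it through.** **Timing.** Inputs: three weeks = 21 days (1.6.1, 1.6.2); biopsy at C1D15 ±1 day, allowed to C1D20 (10.2 and footnote P). The goserelin lead needed before C1D1 is 21 minus the days from C1D1 to biopsy.

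| Biopsy | Days since C1D1 | Lead needed |
|---|---|---|
| C1D14 | 13 | 8 |
| C1D15 | 14 | 7 |
| C1D16 | 15 | 6 |
| C1D20 | 19 | 2 |

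A first dose on C1D1 falls short of 21 days at every allowed biopsy date. A woman who began the agonist with her qualifying therapy has at least 14 + 14 = 28 days by C1D15 and is not affected.

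**The plan's own design figures.** Section 15.3 uses a Simon design: 12 patients, continue with at least 1 arrest; 37 in total, positive with at least 4.

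- Stage 1 stop = (1 − p)^12.
- Go = sum over x from 1 to 12 of P(X1 = x) × P(X2 ≥ 4 − x), with X1 ~ Bin(12, p) and X2 ~ Bin(25, p).
- p = 0.05: stop 0.540, go 0.0935. p = 0.20: stop 0.069, go 0.902.

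These match the stated 54%, alpha 0.1, 7% and 90%.

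**Bias against the regimen (shares assumed).** Let a share g be read unsuppressed with arrest rate c, at a true rate of 20% otherwise. Then p = 0.20(1 − g) + cg.

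| g | c | p | Go | Stage 1 stop |
|---|---|---|---|---|
| 0.05 | 0 | 0.190 | 0.882 | 0.080 |
| 0.05 | 0.05 | 0.1925 | 0.887 | 0.077 |
| 0.05 | 0.10 | 0.195 | 0.893 | 0.074 |
| 0.10 | 0 | 0.180 | 0.857 | 0.092 |
| 0.10 | 0.05 | 0.185 | 0.870 | 0.086 |
| 0.10 | 0.10 | 0.190 | 0.882 | 0.080 |

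The rows with c = 0 are a worst case, since PD 0332991 acts downstream of estrogen.

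**If such women are instead ruled inevaluable and not replaced** (p = 0.20, cut-offs unchanged): one lost gives 0.897 (12+24) or 0.882 (11+25); two lost give 0.891 (12+23), 0.876 (11+24) or 0.857 (10+25).

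**Bias in favor of the regimen (shares assumed).** Let a share g qualify before ovarian suppression and arrest at 44%, the protocol's rate on an aromatase inhibitor alone (1.7, 15.3), while the rest sit at the 5% null. Then p = 0.05(1 − g) + 0.44g.

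- g = 0.05: p = 0.0475 + 0.022 = 0.0695, go 0.216.
- g = 0.10: p = 0.045 + 0.044 = 0.089, go 0.363.

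The false-positive rate rises from 9.3% to 22-36%. The 44% comes from women not selected for Ki67 above 10% on treatment, so it is probably generous here.

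**The case against.** Three objections limit the point.

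*Later safeguards exist.* Section 9.4.5 tests estradiol in premenopausal women at C1D15 without naming a cohort. Section 5.7 recognizes stopping for premenopausal-range estradiol on goserelin. Section 1.9.7 makes a woman inevaluable if estradiol rose to that range during Cycles 1-4. This stands in part. All three act only after PD 0332991 has begun. Section 1.9.7 is written around pre-registration and Cycle 0, which this cohort does not have, and a level that rose does not clearly describe a woman never suppressed. The schedules also differ: 1.9.7 lists Cycle 3 Day 1 but not C1D15, 9.4.5 the reverse, and the 10.2 calendar shows no estradiol test.

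*The exposed group is small.* Three weeks is an upper bound. Section 4.2 bars protocol intervention, not a standard GnRH agonist given earlier, so a first dose on C1D1 is possible and not inevitable. This stands.

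*The omission may be deliberate.* Avoiding delay for a tumor already above 10% is a defensible reason. Section 3.3.1 item 3 still carries "For the endocrine resistant cohort: Ki67 > 10% by central testing" in the same list as the estradiol line, and a reader might infer that the line was dropped by accident when 3.4 was written. The documents do not show this: 3.4.1 item 5 adds a GnRH agonist agreement that 3.3.1 lacks, and 3.4 changes other criteria too. A reader might also infer from the exclusion of prior "Hormonal therapy" in 3.3.2 that 3.3.1 cannot govern this cohort. That fails, because wild type women also have 28 days of anastrozole in Cycle 0. The better grounds are that 3.3 is headed for the wild type cohort and is closed, and that 3.4 is headed for this one.

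A stronger reading is that the gap can only work against the regimen. The documents do not support it, because the qualifying Ki67 may itself have been read without ovarian suppression.

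**Conclusion.** The omission is real and worth correcting, as a low-severity point. A premenopausal woman who starts goserelin less than about 7 days before C1D1 may have her C1D15 Ki67 read before suppression is reliable; for a C1D20 biopsy the margin is about 2 days. This is a risk, not a certainty.

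The net direction of bias is unknown. The ranges above rest on assumed shares of 5-10%, because the documents give no count of such women, and they bound neither effect. The Simon rule itself is correctly calculated and remains valid. The firmer reason to act is individual: a woman could lose study drug, and the adjuvant option, on a reading taken too early.

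**What to change.** 1. Add to 3.4.1 and Appendix B the line the trial already uses, "In premenopausal women, serum estradiol level in postmenopausal range", no more than 7 days before registration.
2. Add an estradiol row for premenopausal women to the 10.2 calendar: before registration, and at C1D15 as 9.4.5 already plans.
3. Report complete cell cycle arrest with and without women whose qualifying Ki67 biopsy was taken before ovarian suppression. The entry line tests estradiol at registration, not at that biopsy, so it does not remove the second bias. This needs the GnRH agonist start date on the worksheet.

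Cost: one eligibility line in two places, one calendar row, one extra blood test per premenopausal woman and one added tabulation. The real downside is delay. Because of Section 4.2, the few unsuppressed women would need up to about 3 weeks of standard off-protocol GnRH agonist before registering, with a tumor already above 10% Ki67.
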